phase. Informed by what stakeholders tell us, we will then work to build Relational Coordination within our hub-and-spoke network to deliver SBIRT-PM.

Within the VA, there are financial incentives for VISN-wide initiatives, such as the one proposed, that bring Veterans into VA care. The formula for funding each VISN is essentially a capitated model of payment per Veteran, called the Veterans Equitable Resource Allocation (VERA). Each additional patient in the New England VISN generates a mean of \$6500⁸⁷ (the median is considerably lower) and Veterans whose conditions are judged to be connected to their military service are, understandably, the highest priority Veterans for VA facilities to enroll. The VA as an organization depends on enrolling new Veterans as those from prior wars die or move to other regions.

Beyond having the potential to improve care for Veterans applying for compensation for MSD-related claims, to the extent SBIRT-PM results in new Veteran enrollment, it could increase revenue into VISN1 and its medical centers. Therefore, our proposal includes a budget impact analysis, with the prosaic but crucial information as to how SBIRT-PM impacts the VISN bottom line. We will determine the cost and cost-effectiveness of SBIRT-PM because these data provide evidence for SBIRT-PM's value.

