4.2 Exclusion Criteria

1. reports inability to participate during the study enrollment call;
2. received three or more non-pharmacological pain treatment modalities within the last 12 weeks from VA (modalities are: (1) acupuncture (2) rehabilitation therapies (3) Manipulation (4) Massage (5) Yoga (6) Tai Chi/Qigong (7) exercise (8) Biofeedback (9) Hypnosis/Hypnotherapy (10) Guided Imagery (11) Meditation (12) Psychotherapy/Counseling (13) Reiki (14) teaching about coping with pain (15) other treatment for pain);
3. participation in another PMC3 study as evidenced by a research protocol alert for that study at the time the study invitation letter is mailed.

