Data for the study are drawn from patient self-report, VA electronic medical records of VA and community care, and the C&P examination. Veterans requesting a Compensation & Pension evaluation for knee, shoulder, neck or back pain may or not be receiving services from the VA. Persons who get all their care outside of the VA will not have readily accessible medical records, while those persons who get some care in the VA but are sent out to community care for distinct services (such as non-pharmacological pain management) will have medical records of both types of care. In addition, those veterans who had not used any VA services prior to their C&P request may then enter VA care following their C&P exam and will have EMR available only in the follow-up period. The lack of EMR data of non-users of the VA will affect both the intervention or control arms of the study, and there is no reason to believe its effect will be differential.

Acknowledging the variability in availability of EMR information, all subjects will have self-reported and C&P data regarding service use as well as diagnoses. We will examine the concordance of self-reported and EMR-obtained information to estimate the impact of having no EMR data in the non-users of the VA. We will conduct a sensitivity analysis sub-setting the analyses only to those persons with available EMR (as well as self-reported and C&P data).

Cost-Effectiveness Analysis

The relative cost-effectiveness of SBIRT-PM will be assessed using both incremental cost-effectiveness ratios (ICERs) and cost-effectiveness acceptability curves (CEACs). ICERs and CEACs will be calculated from the provider (i.e., VISN and medical center) perspective. Using the cost estimates described in the Assessment subsection, we will calculate ICERs for minimal clinically important differences (MCID) between baseline and week-36 assessments in three primary outcomes: self-reported pain, risky alcohol use, and morphine-equivalent doses of opioid analgesic medication use.

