To illustrate the uncertainty associated with ICER point estimates, cost and effect estimates of SBIRT-PM will be bootstrapped (with 2,000 replicates) to produce confidence intervals around the ICERs and to produce CEACs for each outcome measure.¹⁸⁸ CEACs quantify the uncertainty in the cost-effectiveness analysis by showing the probability that the intervention is cost-effective with respect to any given threshold value.¹⁸⁸⁻¹⁹⁰ Intuitively, as the threshold value of a MCID in a given outcome increases, the strategy that produces that effect most efficiently becomes increasingly more likely to be the most cost effective, even though incremental costs are incurred. Similarly, as the threshold value of a MCID in a given outcome decreases, the strategy that has the lowest cost becomes increasingly more likely to be the most cost-effective. Finally, sensitivity analyses will be conducted to determine the robustness of the cost-effectiveness results to alternative assumptions about a wide variety of implementation parameters (e.g., cost of inputs).

Budget Impact Analysis.

To demonstrate the financial feasibility of adopting SBIRT-PM, a budget impact analysis will be conducted. The per-person cost of SBIRT-PM will comprise the cost of delivering the intervention plus the cost of the VA-funded services used by the participant in the SBIRT-PM condition over and above the cost of those used by individuals in UC, minus the yearly patient allocation (VERA dollars) assigned to that participant. The total projected yearly cost to a given medical center of SBIRT-PM will be the per-person cost times the total number of Veterans applying for compensation and pension for a musculoskeletal condition times the expected rate of uptake.

Analyses of NLP Algorithms

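### The budget impact formula nets service costs against usual care but credits SBIRT-PM with the participant's whole VERA allocation, so per-person net cost is understated by the mean allocation per usual-care Veteran

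*Combined protocol and SAP*

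**What the plan says.** Section 9.6 (Budget Impact Analysis) builds the per-person cost of SBIRT-PM from three terms:

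1. the cost of delivering the intervention;
2. the cost of VA-funded services used by the SBIRT-PM participant, counted only "over and above the cost of those used by individuals in UC";
3. a deduction: "minus the yearly patient allocation (VERA dollars) assigned to that participant".

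The result is then scaled up: "The total projected yearly cost to a given medical center of SBIRT-PM will be the per-person cost", multiplied by the number of musculoskeletal claimants and the expected uptake.

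Section 2.2 (Study Rationale) explains why revenue belongs in the analysis, and does so in incremental terms: "to the extent SBIRT-PM results in new Veteran enrollment, it could increase revenue into VISN1 and its medical centers". It also gives the only VERA amount in the document: "Each additional patient in the New England VISN generates a mean of" 6,500 dollars, with the remark that the median is well below this.

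Two places bear on whether UC Veterans carry allocations. The second exclusion criterion in section 4.2 removes only those who "received three or more non-pharmacological pain treatment modalities within the last 12 weeks from VA". Section 9.6 (Sources of data) says that claimants "may or not be receiving services from the VA", and that "those veterans who had not used any VA services prior to their C&P request may then enter VA care following their C&P exam". Neither statement is limited to one arm.

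On timing, section 3 (Costs Estimation Procedures) collects service costs over the 36-week study period. The allocation and the projected medical-center cost in section 9.6 are both yearly.

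**The concern.** A budget impact analysis asks what changes for the payer if the program is adopted, so every term should be the difference between having it and not having it. Delivery cost qualifies, since it is zero under UC. The service term qualifies by construction. The VERA term does not: it is the SBIRT-PM participant's whole allocation.

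Take a Veteran who would have been in VA care in either arm. The formula removes the service cost that this Veteran would have generated under UC but keeps all the revenue that the same Veteran would have brought under UC. The credit therefore goes to SBIRT-PM even when it changed nobody's enrollment.

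With the other terms held fixed, the error runs one way, in favor of SBIRT-PM, in an analysis whose stated purpose is to show that adoption is financially feasible. The medical-center projection then multiplies it by claimants and uptake.

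**Working it through.** The plan states no budget impact figure, so there is nothing to reproduce. The check is an accounting identity followed by an illustration.

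**Notation**
- D = delivery cost per person (no figure in the document).
- dS = mean service cost in SBIRT-PM minus mean service cost in UC (no figure).
- V1, V0 = mean VERA allocation per Veteran in SBIRT-PM and in UC, with zero for a Veteran who has none (no figures).
- V = 6,500 dollars, the mean in section 2.2.
- p_C = share of UC Veterans carrying an allocation (not in the document; assumed).

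**Identity**
- As written: D + dS − V1.
- Fully incremental: D + dS − (V1 − V0).
- Incremental minus as written: V0.

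The understatement is V0 whatever D, dS and V1 are. It is zero only if no UC Veteran carries an allocation.

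**Is V0 above zero?** Section 4.2 lets in Veterans using one or two VA pain modalities, and randomization can place them in either arm. Section 9.6 (Sources of data) describes claimants already in VA care and claimants entering it after the examination. Section 5.1 (Usual Care) withholds no care from controls. Some UC allocation is therefore likely, though its share is unknown.

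**Illustrative size per person, V0 = 6,500 × p_C**

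| Assumed p_C | V0 (dollars) |
|---|---|
| 10% | 6,500 × 0.10 = 650 |
| 50% | 6,500 × 0.50 = 3,250 |
| 90% | 6,500 × 0.90 = 5,850 |

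Two cases show how this works, with assumed shares in both arms:
- 80% of each arm carries an allocation. True added revenue is 0; the formula credits 0.80 × 6,500 = 5,200 dollars per person.
- 50% in UC and 60% in SBIRT-PM. True added revenue is 0.10 × 6,500 = 650 dollars; the formula credits 0.60 × 6,500 = 3,900. The gap is 3,250, which is V0.

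**Illustrative center total.** Section 3 projects 1,448 scheduled Veterans at VA Connecticut over 32 months, or 1,448 × 12/32 = 543 a year. Assume 18% uptake (the pilot enrollment rate in section 3) and p_C = 50%. The yearly understatement is 543 × 0.18 × 3,250 ≈ 318,000 dollars. With p_C from 25% to 75% it is about 159,000 to 476,000.

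**Time basis.** The plan does not say whether the 36-week dS is scaled to a year. Suppose it is used unscaled and the corrected analysis multiplies it by k, from 1.0 (no difference after week 36) to 52/36 = 1.44 (constant rate). Corrected minus planned cost is then V0 + (k − 1) × dS.
- At k = 1.0 this is V0.
- At k = 1.44 it is V0 + 0.444 × dS, which is negative only if dS is below −V0/0.444 = −2.25 × V0. At the three shares tabulated above, that is a service saving of more than about 1,463, 7,313 or 13,163 dollars per person over 36 weeks.

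**The case against.** The best reply is that the formula is a one-sentence summary and should be read with section 2.2, where revenue is tied to additional patients and new enrollment. On that reading the deducted allocation means only money gained through SBIRT-PM. But section 9.6 does not say so. Even if the credit were limited to new enrollees, UC Veterans who enroll after their examination would still have to be subtracted. The reading would shrink the error without removing it, and the wording would still need to change.

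A second objection is that the document does not say who draws a VERA allocation, when, or at what level, so V0 above zero is an inference. That is fair, and it limits what can be said about size. The asymmetry in the formula does not depend on it.

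Third, the dollar figures are soft. The UC shares are assumed. The 6,500 is a mean over New England patients, not musculoskeletal claimants, and the plan itself says the median is considerably lower. Its citation number (87) leads in the reference list to an emergency-department buprenorphine/naloxone trial, so its source cannot be traced. A mean is the right kind of figure for a budget total, but this one serves only as illustration.

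Finally, budget impact is an ancillary analysis with no hypothesis attached. That stands, and it bears on priority. The sensitivity analyses planned in section 9.6 are for the cost-effectiveness results and do not cover this term.

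**Conclusion.** The concern holds. As written, the VERA term is gross while the service term is incremental. Other terms fixed, per-person net cost is understated by V0. That follows from the formula alone. That V0 exceeds zero is an inference from the eligibility rules and the description of claimants' VA use, and a likely one. The range of 650 to 5,850 dollars per person rests on assumed UC shares of 10% to 90% and on the 6,500-dollar mean.

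Because D, dS, V1 and the UC share are not given, no claim can be made that the result would change sign. The unstated time basis is a lesser, related gap. The point should be corrected before analysis. It does not touch the primary outcomes, power, or the cost-effectiveness ratios and acceptability curves.

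**What to change.** In section 9.6 (Budget Impact Analysis), replace the deduction with the between-arm difference in mean yearly VERA allocation, SBIRT-PM minus UC. Count Veterans without an allocation as zero, and estimate the difference in the same participants as the service-cost difference. State that both differences are on a yearly basis, and vary the annualization of the 36-week service-cost difference from ×1.0 to ×1.44 in a sensitivity analysis.

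The cost is a short change of SAP wording before analysis and retrieval of UC participants' allocations from VA administrative data. Trial conduct does not change. The sponsor should accept that the projection may become less favorable to SBIRT-PM, and that annualizing brings in an assumption that has to be shown and varied.

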We will use the customized Resource Allocation Worksheet to estimate the costs of delivering SBIRT-PM from the perspective of the providers (i.e., both the VISN and hospital). Cost estimation for VA services used by Veterans during the 36-week study period will be assessed using national VA administrative databases. Data on service use at the individual patient level will come from the VA National Patient Care Database (NPCD), which includes information on all inpatient and outpatient encounters at VA facilities. Costs for these services will be computed using the VA Average Cost Database, developed by the Health Economics Resource Center (HERC). The Average Cost Database assigns an average cost to each inpatient admission and outpatient visit in VA. Costs are based on Current Procedure Terminology (CPT) codes and can be linked to unique records in the NPCD.

Costs for VA services used by Veterans during the 36-week study period will be assessed using national VA administrative databases. Data on VA service use at the individual patient level will come from the VA National Patient Care Database (NPCD),

which includes information on all inpatient and outpatient encounters at VA facilities. Costs for these services will be computed using the VA Average Cost Database, developed by the Health Economics Resource Center (HERC). The Average Cost Database assigns an average cost to each inpatient admission and outpatient visit in VA. Costs are based on Current Procedure Terminology (CPT) codes and can be linked to unique records in the NPCD. Costs incurred by VA for community care will be obtained from databases tracking payments to community providers.

Procedures to develop a new natural language processing (NLP) algorithm that identifies use of non-pharmacological pain management services

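### The budget impact formula sets a 36-week incremental service cost against a full-year VERA allocation and calls the result yearly, with no rule for weeks 37-52

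*Combined protocol and SAP*

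**What the plan says.** Section 9.6, Budget Impact Analysis, builds a per-person cost from three terms. The first two are delivery and services: "The per-person cost of SBIRT-PM will comprise the cost of delivering the intervention plus the cost of the VA-funded services used" by the SBIRT-PM participant, counted "over and above the cost of those used by individuals in UC". The third is revenue: "minus the yearly patient allocation (VERA dollars) assigned to that participant". The per-person figure is then multiplied up: "The total projected yearly cost to a given medical center of SBIRT-PM will be the per-person cost times the total number of Veterans applying", and by expected uptake.

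That paragraph gives no window for the service term. Section 3, Costs Estimation Procedures, gives one and states it twice, once as "Costs for VA services used by Veterans during the 36-week study period will be assessed using national VA administrative databases". Section 2.2 gives the only VERA amount: "Each additional patient in the New England VISN generates a mean of" $6,500, with the median described as considerably lower. It ties the revenue to new enrollment: "to the extent SBIRT-PM results in new Veteran enrollment, it could increase revenue into VISN1 and its medical centers".

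No section annualises service costs, prorates the allocation, or extracts costs after week 36. The sensitivity analyses in Section 9.6 are specified for the cost-effectiveness results, not for budget impact.

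**The concern.** The revenue term covers 52 weeks, and the service-cost term, as far as the document defines it, covers 36. Adding them gives a figure that belongs to neither period, yet it is labelled yearly.

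The purpose of the analysis is to tell VISN 1 and its centers whether they can afford to adopt SBIRT-PM. The intervention works by starting Veterans on services, some of which may run past week 36. Section 5.1 also allows one more motivational call as late as week 32. Services prompted by that call have about four weeks in which to appear in a 36-week cost window. Any per-person error is then multiplied by all musculoskeletal applicants and by uptake.

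**Working it through.** The document reports no budget impact result, so there is no stated figure to reproduce. The check is arithmetic on the formula.

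**Inputs**
- Service-cost window: 36 weeks (Section 3).
- Revenue window: one year, 52 weeks (Section 9.6).
- V, the VERA amount: $6,500, the mean in Section 2.2.
- C, delivery cost per person: not given; $300 assumed for illustration. All calls end by week 32 (Précis; Section 5.1), so C is fully captured on either horizon.
- D, SBIRT-PM minus UC service cost over 36 weeks: not given; ranged from -$1,000 to $6,000.
- r, the weekly increment in weeks 37-52 divided by the average weekly increment in weeks 1-36: not given; set at 0, 0.5 and 1.

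**Formulas**
- As written: P = C + D - V.
- Matched to 52 weeks: P = C + D × (1 + r × 16/36) - V.
- Amount omitted by the formula as written: D × r × 16/36.

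At r = 1 the factor is 16/36 = 0.444, so 44.4% of D is omitted. At r = 0 nothing is omitted.

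| D | omitted, r = 0 | omitted, r = 0.5 | omitted, r = 1 |
|---|---|---|---|
| -$1,000 | $0 | -$222 | -$444 |
| $500 | $0 | $111 | $222 |
| $1,000 | $0 | $222 | $444 |
| $2,000 | $0 | $444 | $889 |
| $4,000 | $0 | $889 | $1,778 |
| $6,000 | $0 | $1,333 | $2,667 |

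A negative entry means that the formula as written overstates yearly cost. The same happens if D is positive but the increment turns negative after week 36: with D = $1,000 and r = -0.5, the omitted amount is 1,000 × (-0.5) × 16/36 = -$222.

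**Can it change the conclusion?** With C = $300 and V = $6,500, the break-even D is 6,500 - 300 = $6,200 as written. Matched to 52 weeks at r = 1 it is 6,200 / (52/36) = $4,292. At D = $6,000 the per-person result is 300 + 6,000 - 6,500 = -$200 as written, and 300 + 6,000 × 52/36 - 6,500 = +$2,467 when matched. At r = 0 both are -$200. The sign can change, but only with a large and persistent increment. A lower V would lower every break-even value and leave the 44.4% unchanged.

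**A different question: matching to 36 weeks.** Here P = C + D - V × 36/52. The allocation becomes 6,500 × 36/52 = $4,500, which is $2,000 less, whatever D is. This is the answer for a 36-week result, and Section 9.6 does not ask for one.

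**The case against.** The best defence is that the 36-week window is inferred. The budget impact paragraph names no window. The explicit link back to the cost-estimation procedures is made for the cost-effectiveness ratios. The result is called projected, and yearly could refer partly to a year's applicants. This stands as far as it goes: the window is the only one stated, not one attached to this formula. It does not remove the problem. On any of these readings the per-person term still combines a one-year allocation with service costs for which the document provides 36 weeks and no extrapolation rule.

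Three stronger readings are tempting, and the document does not support them.
- *The error always favours adoption.* It does so on the yearly horizon only if the increment after week 36 is positive. At zero there is no error, and with net savings it reverses. The pilot rate ratio of 1.6 in Section 9.2 counts pain-related appointments. It is not a total VA cost and does not show persistence beyond week 36.
- *Each allocated Veteran is over-credited by $2,000.* That holds only if the result is redefined as a 36-week figure. It is not another expression of the 44.4%: if the increment stops at week 36, one is $0 and the other is still $2,000. It also rests on a mean that the document places well above the median.
- *Only 69% (36/52) of a year's costs is counted.* Delivery cost is counted in full. Only the incremental service term can be cut short.

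Whether the allocation should also be netted against UC is a separate question about the same sentence. It is not relied on here, and answering it would not settle the horizon.

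**Conclusion.** The point holds as a horizon mismatch in the incremental service term. Applied with the only service-cost window in the document, the formula omits the SBIRT-PM minus UC service cost in weeks 37-52 from a figure labelled yearly. The omission is $0 if the increment stops at week 36 and 44.4% of the 36-week increment at a constant weekly rate. It changes sign if later weeks bring savings. The 44.4% is not a strict ceiling, since a weekly increment that was still rising at week 36 would exceed it.

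Understatement of yearly cost is the likelier direction, given how the intervention works, but it is not demonstrated. Confidence is high in the mismatch and low in its dollar size, because C, D and r are not in the document. The budget impact analysis is neither a primary nor a secondary outcome. The effectiveness results and the cost-effectiveness ratios are not affected. The change should be made, but it is not critical to the trial's main conclusions.

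**What to change.** Amend the budget impact paragraph of Section 9.6 so that every term covers the same period.

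1. **Preferred.** For this analysis only, extract NPCD, HERC and community-care costs in both arms for 52 weeks from randomisation, and set them against the yearly allocation. Confirm that the data-access approval covers weeks 37-52, because Section 7.2 puts the end of participation at about 36 weeks. Complete the pull before identifiers are removed after extraction and identified files are destroyed at study end (Section 11.3).
2. **If that is not possible.** Keep the yearly allocation and report a 52-week projection. State a scenario range for weeks 37-52, from an increment that stops at week 36 to one that continues at the late-follow-up rate. If the late rate is a net saving, the projection will show it.
3. **Proration.** Multiply the allocation by 36/52 only if the result is relabelled a 36-week budget impact.

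Leave the cost-effectiveness analysis at 36 weeks.

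The cost is a few sentences of text and, for the first option, a longer pull from databases already named, with no participant contact. The budget figure may become less favourable.

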We will adopt a VISN1-wide hub-and-spoke network implementation system in which VA Connecticut Healthcare System will serve as the hub for SBIRT-PM delivery in all eight VISN1 medical centers. The hub will be the site for screening and identifying individuals appropriate for SBIRT-PM, delivering the intervention via telephone to Veterans throughout New England, and referring Veterans to site personnel who make pain management service referrals. This approach has the advantage of fitting the way in which many other clinical interventions and areas of expertise are delivered within VA. One widely used example of a hub-and-spoke model in VHA is SCAN-ECHO (Specialty Care Access Networks-Extension for Community Healthcare Outcomes). In these programs, "hubs" with experts in a particular area arrange teleconferences, trainings, and case consultation for providers in "spokes" or satellite sites. VA Connecticut is the site for a SCAN-ECHO program for pain management, and this model appears to be effective. Suggestive evidence of its effectiveness is that providers who participate in the pain SCAN-ECHO program have been significantly more likely to use physical medicine, anti-depressants, and anti-convulsant treatments, but not opioids.⁷⁸ Other examples are the VA Epilepsy Centers of Excellence to assure increased access to high quality of care for Veterans with epilepsy.⁷⁹ A hub and spoke model has the advantage of being more cost-effective compared to no network from a hospital⁸⁰ and societal perspective.⁸¹ Hub and spoke systems allow for full-time personnel to specialize in the intervention and serve multiple sites, rather than requiring training of larger numbers of personnel at many sites.

[figure not shown]
The theoretical framework for implementation of SBIRT-PM in a hub-and-spoke model is Relational Coordination.⁸² Relational Coordination refers to the quality of communication and collaboration across sites and is predictive of a team's or organization's ability to provide high quality care.⁸³⁻⁸⁵ Hub-and-spoke networks function through collaborative relationships between individuals working across sites.⁸⁶ Information must flow effectively between members of the hub-and-spoke sites for care to be timely, coordinated and appropriate for the patient. In this study, we will first explore how relationships among clinical and administrative staff involved in pain care are coordinated at the sites during baseline semi-structured interviews early in the UG3

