As noted in the completed SBIRT-PM RCT, in only 21 months of recruiting, 1017 examinations (for 1014 unique Veterans) were scheduled for service-connection examinations for back, neck, knee, or shoulder. Over the 32 months of recruitment for the proposed study, this would come to 1448 potentially eligible Veterans at VA Connecticut. To extrapolate from these values to the number of eligible participants we could expect at each of the other seven sites within VISN 1, we used VBA reports of new service-connection examinations requested at each of the other sites for back/neck/knee/shoulder. We then assumed the same proportion at each site would be eligible as were at the Connecticut site.

At VA Connecticut, 257/1014 Veterans met eligibility criteria and enrolled (a 24.3% enrollment rate). The proposed study is likely to enroll at least as high a percentage, and probably higher because: (1) enrollment by phone asks less of Veterans than enrollment in person required in the prior study; and (2) there are fewer inclusion/exclusion criteria in the proposed study. Conservatively assuming the 18% enrollment rate in the UG3 pilot (with only one call to many participants) yields 1862 exceeding the study's randomization goal of 1100. The large sample allows for study completion should recruitment lag at one or more sites.

The large numbers of readily recruitable Veterans in a single VISN speaks to how many Veteran are at risk and engageable at their service-connection examinations.

VISN 1 VA Medical Center	Projected Number of Post-9/11 Veterans Scheduled for MSD Service-Connection Examination over 32 Months of Study
VA Boston	2478
VA Connecticut	1448
Providence, RI	1584
Manchester, NH	1275
Togus, ME	1493
Bedford, MA	744
White River Junction, VT	677
VA Central Western Massachusetts HCS	650
Total	10349

Sources of Materials

Veterans sources of materials:

Information to be collected includes:

1. Veteran questionnaire responses entered into VA REDCap
2. Nail clipping toxicology tests
3. Audio recorded SBIRT-PM sessions
4. Information from the electronic health record (EHR), including the record of the Compensation examinations and service connection determination
5. Service use data from central VA databases

VA Staff sources of materials:

Information to be collected includes:

1. Responses to Relational Coordination Survey
2. Digital recordings of interviews and transcriptions

Assessment Procedures.

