research team explaining the basics of the study and that unless the Veteran opts out, a member of the research team will call to further explain the study. A toll-free phone number will be included in the letter that Veterans can call to opt out of receiving the phone call or to express their interest in participating. A magnet with study contact information and \$1 USD will be included with the recruitment letter. All veterans who are identified as a potential participant and mailed a recruitment letter will receive the magnet and dollar regardless of whether or not they choose to enroll in the study. The magnet is a non-monetary incentive (valued at approximately \$0.21) that will increase response rate, as potential participants can post the magnet in an easy to see location to remind them that the study personnel will be calling. It might also help with retention rates for enrolled participants as it can be a visual reminder of participation and the study team contact information will be readily available. The dollar is a monetary incentive designed to increase the rate at which people will take the study team call. One year into the study, we have found that we are unable to contact 45% of people who are mailed a letter after three contact attempts. Research has shown that pre-paid incentives are most effective at increasing response rate. However, the value of the incentive is nominal so as not to be coercive or to create an undue influence on people from a lower socioeconomic class.

Veterans who opt out will not receive any more study-related phone calls. A copy of the Study Information Sheet describing the study will be included with the recruitment letter.

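### The budget impact formula ties all cost to uptake and has no term for finding and contacting applicants, so it fits at most one uptake rate

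*Combined protocol and SAP*

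**What the plan says.** Section 9.6, Budget Impact Analysis, builds the projection in two steps.

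- Per person: "The per-person cost of SBIRT-PM will comprise the cost of delivering the intervention plus the cost of the VA-funded services used by the participant". Only service use in excess of usual care counts, and the VERA payment is then taken off: "minus the yearly patient allocation (VERA dollars) assigned to that participant".
- Per medical center and year: "the per-person cost times the total number of Veterans applying for compensation and pension for a musculoskeletal condition times the expected rate of uptake". No value is given for the "expected rate of uptake", and the plan does not say whether it is a share of all applicants or of eligible ones.

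The delivery cost has its source in section 3 (Costs Estimation Procedures): "We will use the customized Resource Allocation Worksheet to estimate the costs of delivering SBIRT-PM from the perspective of the providers". The worksheet's items are not listed.

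Section 2.2 describes the service being costed: "The hub will be the site for screening and identifying individuals appropriate for SBIRT-PM". The same sentence names telephone delivery and referral as further hub tasks, so finding candidates is listed apart from delivering the counseling.

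Two passages show how many people the trial's own recruitment has to approach. Section 3 projects enrollment by "Conservatively assuming the 18% enrollment rate in the UG3 pilot", and section 4.3 reports that "we are unable to contact 45% of people who are mailed a letter after three contact attempts".

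**The concern.** Some work is done for every applicant approached, whether or not the Veteran accepts: reviewing the examination schedule, checking who might be suitable, and trying to make contact. Its cost follows the number of applicants. The formula lets cost follow only the number of takers, so an applicant who does not take up SBIRT-PM adds nothing to the total unless that applicant's share has been loaded onto the takers in advance.

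This projection is meant to show a medical center whether it can afford the service. It will be applied center by center, and uptake may differ between centers. A structure that cannot separate per-applicant from per-treated cost will mislead most where uptake is furthest from whatever rate was used to derive the per-person figure. The sensitivity analyses in section 9.6 are attached to the cost-effectiveness results and do not cover this projection.

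**Working it through.** **The plan's own figure.** Section 3 lists eight site projections: 2478 + 1448 + 1584 + 1275 + 1493 + 744 + 677 + 650 = 10349 over 32 months. 10349 × 0.18 = 1862.8, which reproduces the stated 1862. Per year, 10349 × 12/32 = 3881 applicants. The budget impact analysis itself states no numeric result to reproduce.

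**Notation.** N is applicants per year, all taken as approached. u is uptake as a share of N. P is net cost per treated Veteran without outreach. c is identification and outreach cost per applicant approached. The documents give no value for P or c.

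**Formula with and without an outreach term.**
- As written: T = P × N × u.
- With outreach: T′ = c × N + P × N × u.

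**Case A: outreach is not in the per-person cost.** T′ − T = c × N, which is positive for any c > 0. Subtracting VERA dollars may make P negative, but that does not change the sign of the shortfall. The part due to non-takers is c × N × (1 − u).

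**Case B: outreach is averaged into the per-person cost at some uptake u0.** The loaded cost is P + c/u0, so T = P × N × u + c × N × u/u0. The error is T − T′ = c × N × (u/u0 − 1). It is zero at u = u0, negative below and positive above.

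Illustration with assumed P = $300, c = $25 and u0 = 18%. The loaded cost is 300 + 25/0.18 = $438.89. N cancels, so results are per applicant:

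| Uptake | Formula as written | Separate outreach term | Error |
|---|---|---|---|
| 10% | 438.89 × 0.10 = $43.89 | 300 × 0.10 + 25 = $55.00 | −20% |
| 18% | $79.00 | $79.00 | 0 |
| 40% | 438.89 × 0.40 = $175.56 | 300 × 0.40 + 25 = $145.00 | +21% |

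**Staff time, as a rough scale for Case A.** Non-takers per taker are (1 − u)/u.
- At the 18% pilot enrollment rate: 0.82/0.18 = 4.56. At an assumed 10 to 30 staff minutes each, that is 46 to 137 minutes per taker.
- Scheduled counseling in the first 12 weeks (Précis): 60 + 3 × 20 = 120 minutes at most. 46/120 = 38% and 137/120 = 114%.
- At the earlier trial's count in section 3, 257/1014 = 25.3% (the text prints 24.3%): 757/257 = 2.95 non-takers per taker, so 29 to 88 minutes, or 25 to 74% of 120.

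**The case against.** The strongest reply is that the worksheet is customized and takes the VISN and hospital perspective, and that identification is a hub function, so its cost may already be in the delivery figure. If so, nothing is lost at the uptake where it was averaged. This stands: a reader might infer that non-takers are costed at zero and that the yearly cost is therefore too low, but the documents do not show either. The reply does not rescue the formula at other uptakes, where Case B applies.

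Four further objections also stand:

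- **Enrollment is not uptake.** A reader might infer that four in five applicants would decline the service. The 18% is enrollment in a research pilot, reflecting trial eligibility and research consent, with many Veterans called only once. The mailings, the dollar bill, the magnet and the research assistants' calls are trial recruitment, and nothing says that routine SBIRT-PM would use them.
- **Eligibility.** A missing eligibility factor is not shown. Uptake taken as a share of all applicants can already include it. Only the denominator is undefined.
- **Cost-effectiveness ratios.** A reader might want outreach added to the incremental ratios. In the trial it precedes randomization and falls on both arms, so it is not an incremental within-trial cost.
- **Comparator.** The 120 minutes leave out the week 12 to 32 call, coordination with primary care, progress notes and supervision, so the percentages overstate the share of total staff time.

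**Conclusion.** The point holds as one of structure. A cost that scales with applicants has no term, and the plan does not say where it sits. The direction is certain only if outreach is outside the per-person cost: the yearly total is then too low. If outreach is averaged in, the error is zero at one uptake and takes either sign elsewhere.

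The size cannot be set from the documents. The 38 to 114% rests on 18% uptake and on 10 to 30 minutes per applicant, both assumptions. It is a share of counseling time, not of net budget impact, which also contains excess VA services and the VERA offset. The only outreach items with prices in the documents are the dollar and the magnet, 1.00 + 0.21 = $1.21 per letter (section 4.3), and these are research incentives.

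The correction is worth making because the financial case for adoption rests on this projection. It does not touch the primary outcomes, the sample size or the validity of the trial.

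**What to change.** In section 9.6, replace the total by:

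yearly cost = (identification and outreach cost per applicant × applicants approached) + (per-treated net cost × applicants × uptake).

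Then:

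- State that outreach is kept out of the per-treated cost, and list what the worksheet's delivery cost contains.
- Exclude letters and incentives used only for research.
- Define uptake as the share of all applicants who are eligible and accept, or multiply by an explicit eligible share.
- Take contact attempts from the screening records. Section 5.4 has counselors log session duration, but section 10.1 does not describe staff time on the research assistants' form, so vary minutes per attempt over a stated range.
- Vary uptake with outreach cost held per applicant.

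Leave the cost-effectiveness ratios unchanged on this account.

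The cost is a few lines of SAP text and some extra costing work, with no new patient data. The projected cost may become less favorable to SBIRT-PM.
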